3.4.2 Documentation of Consent

The Principal Investigator or IRB approved sub-investigator will be responsible for documentation in the medical record that consent has been obtained from all participants. A signed copy of the consent form will be given to each participant. Original consent forms will be stored in the subject's medical chart.

3.4.3 Demographic/Medical History/Current Medical Conditions, and Laboratory Abnormalities

Demographics and medical history will be obtained by the Investigator or designee during the Screening Period. Demographics will include date of birth, sex, ethnicity, and race. Relevant medical history should be recorded and should include prior/current medical conditions, and clinically significant laboratory abnormalities (excluding study disease-related abnormalities). All prior treatment for melanoma will be recorded. All non-melanoma medications used during the 28 days before the first dose of the study drugs will be recorded.

3.4.4 Review Inclusion/Exclusion Criteria Including Concomitant Medication

Inclusion and exclusion criteria will be reviewed by the Investigator to ensure that the subject qualifies for the study at Screening. All appropriate medication washout times will be discussed with the subject and documented; the ICF must be signed before discontinuing any medication.

3.4.5 Registration Procedures

3.4.5.1 General Guidelines

Each patient must sign and date an informed consent form before undergoing any study specific procedure unless a procedure is being performed as part of the patient's standard of care.

Enrollment in the study requires that all inclusion and exclusion criteria have been met. Enrollment occurs upon confirmation of registration from the NYULMC PCC Clinical Trials Office. The following materials must be submitted to the Research Coordinator for registration:

1. Complete signed and dated informed consent form
2. Complete signed and dated informed consent checklist
3. Complete signed and dated eligibility checklist
4. All supporting documentation verifying each criterion has been met

Registration will occur within 24 hours of research coordinator receipt of all of the above documents. A written confirmation of enrollment including a unique study identification number assigned by the research coordinator will be distinguished to the study team upon registration.

Pretreatment evaluation will therefore be as directed by standard clinical practice. Eligible subjects will be entered on study by the study coordinator.

All patients will be required to sign a written informed consent prior to being registered on this study. Every effort will be made to answer questions raised by patients and their families or advocates regarding the protocol and alternative therapies prior to asking a patient to sign the consent form.

Once eligibility is verified, a unique patient study number will be issued within 24 hours of receiving all required registration material. The patient will not be identified by name. This is the point, at which, the patient is considered on study. Subjects must not start any protocol procedures prior to registration.

3.4.6 Early Discontinuation Criteria and Procedures

3.4.6.1 Discontinuation of Study Drug

It is the right and duty of the Investigator to discontinue the study drugs of any subject if he feels that discontinuation of the study drugs is necessary to protect the subject, or that there are unmanageable factors that may interfere significantly with the study procedures and/or the interpretation of results.

Administration of the study drugs will be discontinued if the subject develops a DLT, documented relapse, or other intolerability to the study drugs.

Administration of the study drugs may be discontinued during the study for any of the following reasons:

- Adverse event(s)
- Protocol violation
- Subject withdrew consent
- Lost to follow-up
- Other
- Death

For subjects who discontinue the study drugs for any reason, the remaining study visits and associated evaluations (without dosing) should be completed. Patients who discontinue the study drug(s) due to a toxicity will be followed until the toxicity resolves to baseline. Patients will continue to be followed on the protocol schedule for radiology assessments and for relapse free survival. Pharmacokinetic samples will only be collected at the visit following study drug discontinuation.

All subjects will be followed for adverse events for at least 70 days after the last dose of study drugs and for survival follow-up indefinitely until withdrawal of consent or death.

3.4.6.2 Discontinuation from the Study

Subject participation in the study may be discontinued for any of the following reasons:

- Adverse event(s)
- Protocol violation
- Subject withdrew consent
- Lost to follow-up
- Disease relapse

-
- Death
 - Other

For subjects who discontinue the study for any reason, all evaluations associated with the Study Completion/Early Withdrawal visit should be performed. All subjects will be followed for adverse events for at least 70 days after the last dose of study drugs.

If a subject withdraws consent for study participation, every attempt will be made to determine the reason. These subjects will be asked to allow survival follow-up contacts. Subject completion status (completed versus not completed) will be documented.

For subjects who discontinue from the study without completing the Study Completion/Early Withdrawal visit, only study drug-related adverse events will be collected.

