6.3.3. Safety

The safety analysis will be conducted on the Safety Population. The following safety parameters will be evaluated: adverse events, clinical laboratory tests, physical examinations, vital signs, ECOG performance status, ECGs, chest radiographs, immune safety, and immunogenicity. All safety parameters will be summarized using descriptive statistics.

- **Adverse Events**

Treatment-emergent adverse events (TEAEs) are defined as signs or symptoms that emerge during treatment or within 100 days of the last dose of study drug, including those signs and symptoms that have been absent pre-treatment or that have worsened relative to the pre-treatment assessment. Any adverse event considered related to treatment will also be considered a treatment-emergent adverse event (TEAE), regardless of the elapsed time since the last dose of study drug.

An irAE, a subset of adverse events, is defined as a clinically significant adverse event of any organ that is associated with study drug exposure, of unknown etiology, and is consistent with an immune-mediated mechanism.

All adverse events recorded during the study will be summarized using descriptive statistics. The incidence of TEAEs will be summarized by body system, preferred term, verbatim of adverse event, intensity (based on CTCAE Version 4.0 grade), and relationship to each study drug (NIVOLUMAB and/or the ipilimumab).

- **Vital Signs**

The observed vital signs at each visit and the change from baseline to each post-baseline visit will be summarized by cohort using descriptive statistics.

- **Physical Examination**

Abnormal findings in physical examination will be summarized using descriptive statistics.

- **Clinical Laboratory Tests**

Clinical laboratory test values outside the normal range and clinically significant abnormal range will be flagged in the data listing.

Laboratory data will be summarized using shift tables (baseline to notable post-baseline visit). The change from baseline will be summarized using descriptive statistics.

- **ECOG**

The data observed from ECOG performance status will be summarized appropriately.

- **Other Safety Evaluations**

The results of ECGs, chest radiographs, immune safety tests, and immunogenicity will be summarized appropriately.

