6.8. Reporting of Serious Adverse Events and Unanticipated Problems

Following the subject’s written consent to participate in the study, all SAEs, whether related or not related to study drug, must be collected, including those thought to be associated with protocol-specified procedures. All SAEs must be collected that occur within 100 days of discontinuation of dosing. CTCAE version 4.03 terms should be used.

The collection of nonserious AE information should begin at initiation of study drug. All nonserious adverse events (not only those deemed to be treatment-related) should be collected continuously during the treatment period and for a minimum of 100 days following the last dose of study treatment. Additionally, any SAE or other AE of concern that the investigator believes may be related to study treatment and that occurs later than 30 days after last study treatment should be reported. Information for any non-serious AE that starts during the treatment period or within 70 days after last treatment will be collected from the time of the event until resolution of the event, or until the patient’s last study visit, whichever comes first. Serious adverse event information will be collected until the event is considered chronic and/or stable.

All fatal or life-threatening adverse events must be immediately reported to the Sponsor-investigator by telephone or e-mail. Within 24 hours of the event, the Serious Adverse Event (SAE) Form supplied by NYULMC must be faxed to the Sponsor-investigator and BMS, who must then inform the NYULMC IRB, PCC CTO, and DSMC within 24 hours of the event whether full information regarding the event is

known or not. Additional follow-up by the investigator will be required if complete information is not known. De-identified source documentation of all examinations, diagnostic procedures, etc. which were completed with respect to the event should be included with the SAE form. Care should be taken to ensure that the patient's identity is protected and the patient's identifiers (as assigned at the time of study enrollment) are properly mentioned on any copy of source document provided to the Sponsor-investigator. For laboratory results, include the laboratory normal ranges.

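### For subjects who leave without the final visit, section 3.4.6.2 collects only drug-related adverse events; this contradicts section 6.8 and can only lower all-causality event rates

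*Combined protocol and SAP*

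**What the plan says.** Four places in the combined protocol and SAP govern which adverse events are collected and counted.

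- **Section 3.4.6.2 (Discontinuation from the Study), restriction.** "For subjects who discontinue from the study without completing the Study Completion/Early Withdrawal visit, only study drug-related adverse events will be collected".
- **Section 3.4.6.2, general follow-up.** Just before that sentence, with no limit by causality: "All subjects will be followed for adverse events for at least 70 days after the last dose of study drugs". Section 3.4.6.1 has a similar 70-day statement for subjects who stop study drug.
- **Section 6.8 (Reporting of Serious Adverse Events and Unanticipated Problems).** On nonserious events: "All nonserious adverse events (not only those deemed to be treatment-related) should be collected continuously during the treatment period", and also "for a minimum of 100 days following the last dose of study treatment". On serious events: "all SAEs, whether related or not related to study drug, must be collected", with the window "All SAEs must be collected that occur within 100 days of discontinuation of dosing". Section 6.8.2 repeats the rule for serious events. Neither section makes an exception for subjects who leave the study.
- **Section 6.3.3 (Safety).** Treatment-emergent adverse events (TEAEs) are "signs or symptoms that emerge during treatment or within 100 days of the last dose of study drug", so the definition rests on timing. An event judged related also counts however late it occurs. The analysis rule is "All adverse events recorded during the study will be summarized using descriptive statistics", and TEAEs are also tabulated by relationship to each drug.

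The denominator is the Safety Population of section 6.2.1, which is everyone who received any part of a dose. Table 1 puts the completion/early-withdrawal visit about 12 weeks after the last dose.

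**The concern.** Section 3.4.6.2 uses the relatedness judgement to decide what enters the database. Section 6.8 and the TEAE definition use it only to classify events that have already been collected. A site cannot follow both for the same subject.

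The primary objective is safety and tolerability, and the trial has a single open-label arm. If an unrelated event in an early leaver is not recorded, no analysis can recover it. Attribution can also change: section 6.10 calls an event immune-related only after efforts to rule out other causes. An event first put down to infection, and therefore not collected, could not be reclassified later. The conservative imputation principle in section 6.4 is illustrated with a missing onset day and gives no rule for events that were never collected. No planned table shows how many subjects had incomplete ascertainment.

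**Working it through.** The documents state no adverse event rate and no figure for this point, so there is nothing to reproduce. The check compares the texts, then derives the direction and unit size of the bias.

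**1. The rules side by side, for a dosed subject who leaves and misses the final visit**

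| Event between study exit and day 100 after last dose | 3.4.6.2, restriction | 3.4.6.2, 70-day sentence | 6.8 | Counts as TEAE under 6.3.3 |
|---|---|---|---|---|
| Drug-related | collected | collected to at least day 70 | collected | yes |
| Unrelated, nonserious | not collected | collected to at least day 70 | collected | yes |
| Unrelated, serious | not collected | collected to at least day 70 | collected | yes |

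The conflict is in the two unrelated rows. Section 6.11 adds to it. It asks for expedited reporting of diarrhea/colitis of Grade 2 or higher with no relatedness condition, and of motor neurologic toxicity of Grade 3 or higher whatever the cause.

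**2. How much of the window is filtered**

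If a subject leaves e days after the last dose, the restriction covers 100 − e days of the TEAE window. Leaving straight after a dose (e = 0) filters 100 days. Leaving at the nominal time of the missed visit (12 × 7 = 84 days) filters 100 − 84 = 16 days. The restriction therefore overlaps the TEAE window even if it is read as covering only the time after exit.

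**3. Direction**

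Let N be the number dosed, x the number with at least one qualifying event of any cause, and m the number whose only qualifying event is unrelated and falls between exit and day 100. The true proportion is x/N and the reported one is (x − m)/N. The bias is −m/N, which is never positive. For drug-related events m = 0 by construction, so those rates are not directly lowered. Dose-limiting toxicities are defined as drug-related in section 4.2.4.1, so the stopping rule in section 4.2.5 is not directly affected either.

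**4. Size per subject**

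Sections 4.3 and 6.1 give 20 and 25 as the planned numbers.

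- N = 25: each missed subject costs 1/25 = 4 percentage points.
- N = 20: each missed subject costs 1/20 = 5 percentage points.

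**5. Assumed range for the total**

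The value of m is not in the documents. Assume k leavers without the final visit, a true all-causality rate q of 0.3 to 0.8, and a share r of those subjects (0.3 to 0.8) who also have a drug-related event. The expected loss is k·q·(1 − r)/N.

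- k = 5, N = 25: from 5 × 0.3 × 0.2/25 = 1.2 points to 5 × 0.8 × 0.7/25 = 11.2 points. At q = r = 0.5 it is 5 × 0.5 × 0.5/25 = 5.0 points.
- k = 3, N = 20: from 3 × 0.3 × 0.2/20 = 0.9 points to 3 × 0.8 × 0.7/20 = 8.4 points.

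The formula treats a leaver's whole record as filtered, so for the post-exit reading these figures are on the high side. They illustrate scale and do not estimate the bias.

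**The case against.** The strongest reply is that the sentence is narrow.

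- It most naturally governs the time after study exit. Section 4.6 has a parallel limit on concomitant medication that says so expressly. Events before exit should already have been recorded.
- Stopping drug is not leaving the study. Section 3.4.6.1 keeps such subjects on their remaining visits and follows toxicities until they return to baseline.
- Many who leave and also miss the final visit will be lost, will have withdrawn consent or will have died, so fuller collection is often impossible.
- Sections 6.8, 6.8.2 and 6.11 still require serious events and several special-interest events.

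All of this stands, and it limits the point to unrelated, mainly nonserious events after exit. It does not remove the contradiction. The sentence is not confined to subjects who cannot be reached: adverse event, relapse and protocol violation are also listed reasons for leaving. Someone must hear of an event before judging whether it is related, so the restriction saves little work.

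Three stronger readings are tempting and are not supported.

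- **The primary safety rates fall.** No section names all-causality incidence as the primary summary. Section 6.3.3 also tabulates by relationship and specifies no separate serious-event rate.
- **The loss falls mainly on those who tolerated treatment worst.** This is possible, but the visit rules above mean the documents do not show it.
- **The all-causality rate drops by 4 to 20 points.** The upper end, 5/25, treats all five extra places as dosed leavers who each had only a missed event. Section 6.1 mentions screening failures, and section 4.9 replaces untreated subjects. Neither group is in the Safety Population.

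**Conclusion.** Section 3.4.6.2 is wrong as written. It is an internal contradiction of moderate severity. If it is followed, all-causality TEAE rates can only be biased downward; so can counts of serious events, if it is given precedence over section 6.8. An unrelated event missed in this way cannot be reassessed.

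The total size cannot be computed from the documents, and it is zero if no dosed subject has such an event as the only qualifying one. The conclusion on direction needs no assumption about rates. It needs only that the restriction is applied between exit and day 100, and that the Safety Population keeps the subject.

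**What to change.** 1. Delete the restricting sentence in section 3.4.6.2. State instead that adverse events and serious adverse events of any causality are collected for every dosed subject through 100 days after the last dose, by telephone or from medical records where visits are missed, unless consent for follow-up is withdrawn or contact is lost.
2. State that after day 100 only drug-related events are collected, together with the procedure-related serious events that section 6.8.2 already requires.
3. Write the 100 days into the text. A cross-reference to section 6.8 would be ambiguous, because that section uses 100, 70 and 30 days for different purposes. Align the 70-day statements in sections 3.4.6.1, 3.4.6.2 and 6.8 with the 100-day window.
4. In the section 6.3.3 safety tables, report how many subjects have an incomplete collection window.

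The cost is a short amendment and a few extra contacts. All-causality rates may look slightly less favourable.

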4. TREATMENTS

On days when both study drugs will be administered, NIVOLUMAB will be administered before starting the ipilimumab infusion.

4.1. Description of NIVOLUMAB with ipilimumab Treatment

NIVOLUMAB will be supplied as a sterile, preservative-free solution in 10 mL vials at a concentration of 10 mg/mL; which, based on the subject's weight, may be diluted with sterile normal saline (0.9% sodium chloride). NIVOLUMAB (1, 3, or 10 mg/kg) will be administered as a 30-minute i.v. infusion. Although NIVOLUMAB has been infused generally over 60 minutes, a series of 20 patients have received the drug at 3 mg/kg or 10 mg/kg over 30 minutes without any increase in infusion reactions. Therefore, it is felt safe to administer NIVOLUMAB in this study over 30 minutes.

Ipilimumab will be supplied as a sterile, preservative-free solution in 40 mL (200 mg) vials at a concentration of 5 mg/mL; which, based on the subject's weight and dose level assignment, may be diluted with sterile normal saline (0.9% sodium chloride). Ipilimumab (3 mg/kg) has been administered as a 90-minute i.v. infusion. Since ipilimumab will be given at 1 mg/kg in this study, one third the dose previously used, it is felt appropriate to shorten the 90 minute infusion to 30 minutes, since the infusion rate will not change.

BMS, Inc. will manufacture and supply NIVOLUMAB and ipilimumab to the Sponsor-investigator.

4.2. Treatment Regimen

4.2.1 Toxicity management

4.2.1.1. Management:

For Grade 1 and 2 adverse events felt due to NIVOLUMAB or NIVOLUMAB with ipilimumab, symptomatic treatment is called for generally without a dose delay. For selected irAEs of grade II, especially colitis and ophthalmologic toxicity, one dose of NIVOLUMAB or NIVOLUMAB with

ipilimumab may be skipped until resolution of the toxicity to Grade 1 or less. Grade 3 irAEs that constitute dose limiting toxicity will cause treatment with NIVOLUMAB or NIVOLUMAB with ipilimumab to be discontinued permanently. For grade III irAEs that do not constitute DLT, do not require more than 2 weeks of systemic steroid treatment, and resolve within 28 days to grade I or less, with either one or no skipped doses, therapy with NIVOLUMAB or NIVOLUMAB with ipilimumab may continue at the same dose(s). There will be no dose reductions of NIVOLUMAB for an individual patient. Management of infusion reactions is defined in section 5.2.2 below.

4.2.1.2. Dose Delay:

NIVOLUMAB with ipilimumab administration should be delayed for the following:

- Any Grade ≥ 2 non-skin, drug-related adverse event, with the following exceptions:
 - Grade 2 drug-related fatigue or laboratory abnormalities do not require a treatment delay
- Any Grade 3 skin, drug-related adverse event
- Any Grade 3 drug-related laboratory abnormality, with the following exceptions for AST, ALT, total bilirubin, amylase and lipase:
 - If a subject has a baseline AST, ALT, or total bilirubin that is within normal limits, delay dosing for drug-related Grade ≥ 2 or greater toxicity
 - If a subject has baseline AST, ALT, or total bilirubin within the Grade 1 toxicity range, delay dosing for drug-related Grade ≥ 3 or greater toxicity
 - Grade 3 amylase or lipase abnormalities that are not associated with symptoms or clinical manifestations of pancreatitis do not require a dose delay. It is recommended to consult with the BMS Medical Monitor for Grade 3 amylase or lipase abnormalities.
- Any adverse event, laboratory abnormality, or intercurrent illness which, in the judgment of the investigator, warrants delaying the dose of study medication.

Because of the potential for clinically meaningful nivolumab or ipilimumab related AEs requiring early recognition and prompt intervention, management algorithms have been developed for suspected pulmonary toxicity, GI, hepatotoxicity, endocrinopathy, skin toxicity, neurological toxicity and nephrotoxicity. For the overlapping adverse event management algorithms present in both the NIVOLUMAB and ipilimumab IB (**GI, hepatic, and endocrine** algorithms), the recommendations are to follow the NIVOLUMAB IB adverse event algorithms as opposed to the ipilimumab IB algorithms.

Subjects may resume treatment with study drug (s) when the drug-related AE(s) resolve to Grade 1 or baseline value, with the following exceptions:

- Subjects may resume treatment in the presence of Grade 2 fatigue

-
- Subjects who have not experienced a Grade 3 drug-related skin AE may resume treatment in the presence of Grade 2 or less skin toxicity
 - Subjects with baseline Grade 1 AST/ALT or total bilirubin who require dose delays for reasons other than a 2-grade shift in AST/ALT or total bilirubin may resume treatment in the presence of Grade 2 AST/ALT OR total bilirubin
 - Subjects with combined Grade 2 AST/ALT AND total bilirubin values meeting discontinuation parameters should have treatment permanently discontinued
 - Drug-related pulmonary toxicity, diarrhea, or colitis, must have resolved to baseline before treatment is resumed
 - Drug-related endocrinopathies adequately controlled with only physiologic hormone replacement may resume treatment

If the criteria to resume treatment is met, the subject should restart treatment at the next scheduled timepoint per protocol. However, if the treatment is delayed past the next scheduled timepoint per protocol, the next scheduled timepoint will be delayed until dosing resumes. If treatment is delayed greater than 6 weeks, the subject must be permanently discontinued from study treatment, except as specified in the discontinuation section below.

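### For drug-related Grade 2 non-skin clinical events in Cycle 1, section 4.2.1.1 generally continues dosing and section 4.2.1.2 delays it, with limited exceptions, and nothing says which governs

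*Combined protocol and SAP*

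**What the plan says.** Section 4.2.1.1 (Management) covers nivolumab alone and the combination. For Grade 1 and 2 events attributed to treatment, "symptomatic treatment is called for generally without a dose delay". For a selected group of Grade 2 immune-related adverse events (irAEs), with colitis and eye toxicity named, one dose "may be skipped until resolution of the toxicity to Grade 1 or less". Infusion reactions are sent elsewhere: "Management of infusion reactions is defined in section 5.2.2 below" (that material is now numbered 4.2.2).

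Section 4.2.1.2 (Dose Delay) opens with "NIVOLUMAB with ipilimumab administration should be delayed for the following". The first item on its list is "Any Grade ≥ 2 non-skin, drug-related adverse event", qualified by "Grade 2 drug-related fatigue or laboratory abnormalities do not require a treatment delay". A later item, for subjects whose AST, ALT or total bilirubin was normal at baseline, says to "delay dosing for drug-related Grade ≥ 2 or greater toxicity". The section then sets resumption criteria. The general threshold is Grade 1 or baseline. One exception is stricter: "Drug-related pulmonary toxicity, diarrhea, or colitis, must have resolved to baseline before treatment is resumed". Another is looser: an endocrinopathy held in check by physiologic hormone replacement alone does not bar dosing.

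The synopsis adds a third wording: a Grade 2 irAE that has not settled to Grade 1 by the infusion day might mean leaving out a dose. The only precedence statement nearby ranks the nivolumab Investigator Brochure algorithms above the ipilimumab ones. It does not rank 4.2.1.1 against 4.2.1.2.

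**The concern.** The two sections are adjacent, address the same patient on the same infusion day, and point in opposite directions. Under the first, a Grade 2 non-skin clinical event is treated and dosing goes on as a rule. Under the second, dosing waits. Neither refers to the other.

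Safety and tolerability are the primary objective. Read alone, 4.2.1.1 allows both checkpoint inhibitors to be infused again while such an event is unresolved. The protocol treats one of these events, diarrhea or colitis of Grade 2 or higher, as serious enough for 24-hour reporting to BMS (2.4.2) and, when drug-related, at least weekly in-person visits (6.10). What is at stake is patient safety and the timing of Cycle 1 doses.

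**Working it through.** The plan gives no figure to reproduce, so the check is a comparison of texts followed by simple bounds.

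**Which events are in conflict.** Combination dosing occurs only in Cycle 1 (Table 1, footnote 11), so the comparison is limited to that cycle.

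| State on the infusion day | 4.2.1.1 | Other text | Conflict? |
|---|---|---|---|
| Grade 2 non-skin clinical event, e.g. arthralgia | Dose, as a rule | 4.2.1.2: delay | Yes |
| Grade 2 colitis | Skip optional, until Grade 1 or less | 4.2.1.2: delay, resume at baseline | Yes, on trigger and threshold |
| Pulmonary toxicity, diarrhea or colitis at Grade 1 after a delay, not yet baseline | Dose | 4.2.1.2: wait | Yes |
| Grade 2 AST, ALT or bilirubin from a normal baseline | Dose, as a rule, if it is an adverse event | 4.2.1.2 liver-test item: delay | Only if it counts as an adverse event (5.1.6, 6.6) |
| Grade 2 skin event, fatigue or other laboratory change | Dose | 4.2.1.2: no delay required | No |
| Infusion reaction | Refers elsewhere | 4.2.2 | No |
| Endocrinopathy controlled by hormone replacement alone | Dose | 4.2.1.2: may resume | No |
| Grade 2 eye event needing systemic treatment, or neither responding to topical therapy nor improving to Grade 1 | Skip optional | 4.2.1.3: permanent stop | Outside: 4.2.1.3 decides |
| irAE treated with more than 10 mg/day prednisone in the prior 2 weeks | No dose | 4.6.1: no dose | No |

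In the last row, 4.6.1 bars the infusion whichever of the two sections is followed.

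**Ceiling on decisions.** Cycle 1 infusions fall on days 1, 22, 43 and 64 (Table 1), an interval of 22 − 1 = 21 days. Re-dosing decisions per patient are 4 − 1 = 3. Across the trial that is 3 × 20 = 60, or 3 × 25 = 75 at full enrollment. Only the decisions that meet a row marked yes, or the conditional liver-test row, are affected.

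**Doses at stake if dosing waits (4.2.1.4).**
- Delay of 1 to 7 days: the visit is made up, so 0/4 doses are lost.
- Delay of 8 to 21 days: one dose is missed, 1/4 = 25%.
- Longer delay: once it passes the next infusion's own 7-day allowance (21 + 7 = 28 days), a second dose is missed, 2/4 = 50%.
- Delay over 35 days: study drug stops. If the hold began after dose 1, doses 2 to 4 are lost, 3/4 = 75%.

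Section 4.2.1.2 describes a long delay differently: the next timepoint moves until dosing resumes, and the dose is not said to be lost. Its limit is 6 weeks, subject to 4.2.1.3. The dose losses above therefore apply if 4.2.1.4 is followed.

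**The case against.** The best answer is that the sections can be reconciled. Section 4.2.1.1 is hedged by the word generally, and 4.2.1.2 is the detailed list for the combination. A site that delays under 4.2.1.2 breaches nothing in 4.2.1.1, and reading the general before the specific is natural. This has force: a reader might infer that the plan directs sites to re-dose through Grade 2 colitis, and it does not. It makes the skip optional in one place and calls for a delay in another.

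The hedge still does not settle the rule. Section 4.2.1.1 states its own exception, which is narrower (selected irAEs) and permissive, while 4.2.1.2 takes in any non-skin event beyond its short list of exceptions. Colitis is the clearest case: the sentence naming it is not qualified by generally, and both the trigger and the resumption threshold differ from 4.2.1.2.

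Existing safeguards narrow the gap: investigator discretion to delay, the management algorithms, the steroid-taper rule in 4.6.1, the eye-toxicity rule in 4.2.1.3 and pre-dose laboratory review in 5.1.6. None says which section governs. Discretion only adds reasons to delay, and laboratory review will not detect arthralgia or colitis. The Investigator Brochure algorithms might close more of the gap, but they cannot be seen here.

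A further objection is that a repair confined to Cycle 1 could suggest that nothing similar applies to nivolumab alone, which is given about 48/4 = 12 times afterwards. That is a fair caution, and the fix answers it.

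**Conclusion.** The inconsistency is real and should be corrected, within the limits in the table. It concerns Cycle 1 combination dosing and drug-related Grade 2 non-skin clinical events, plus liver-test changes that qualify as adverse events, and it leaves out the groups listed there.

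Its ceiling is 60 decisions in 20 patients or 75 in 25. A reader might take these as a forecast. They are not: the documents give no Grade 2 frequency for this regimen, so no patient count is offered. Under 4.2.1.4 the dose consequence of waiting runs from 0 to 1 of 4 doses for delays up to 21 days, and up to 3 of 4 for a prolonged hold after dose 1.

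A reader might also infer that the stopping rule or the safety analysis is compromised. The documents do not support that. The dose-limiting toxicity definition in 4.2.4.1 counts Grade 3 or higher events, and the summaries in 6.3.3 do not depend on the delay rule. Nor does the point reach cycles 2-5, since the lead-in to 4.2.1.2 names only the combination.

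The conclusion rests on the text alone and assumes that no document outside this one ranks the two sections.

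**What to change.** - State that in Cycle 1, section 4.2.1.2 governs, with its resumption criteria (including the endocrinopathy exception) and 4.2.1.3.
- For Cycle 1, reword 4.2.1.1 along these lines: *Grade 1 events, and Grade 2 events for which 4.2.1.2 does not call for a delay, are treated symptomatically without delaying the dose unless the investigator judges a delay warranted; all other Grade 2 events follow 4.2.1.2 and 4.2.1.3.* Infusion reactions stay under 4.2.2.
- For Cycle 1, replace the optional-skip sentence in 4.2.1.1 and the Grade 2 irAE sentence in the synopsis with a reference to 4.2.1.2.
- State that the Cycle 1 wording does not limit the resumption criteria for nivolumab alone in cycles 2-5. Whether the delay rule should also apply there is for the sponsor to decide.
- Optional tidying: in the first item of 4.2.1.2, exempt Grade 2 laboratory abnormalities other than AST, ALT and total bilirubin, which have their own item.

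The change adds no visits and no data. Its cost is that some Cycle 1 doses that 4.2.1.1 would have allowed will be delayed or missed: under 4.2.1.4, 0 to 1 of 4 for delays up to 21 days, and up to 3 of 4 after a prolonged hold. The fix does not resolve the difference between 4.2.1.2 and 4.2.1.4 over whether a delayed dose is lost. As a safety-related amendment it needs IRB, BMS and NCI CTEP approval (12.2).
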